3.1. IMWG Criteria

According to IMWG criteria, response categories include complete response (CR), stringent complete response (sCR), very good partial response (VGPR), partial response (PR), stable disease (SD), and progressive disease (PD) (defined in Section 1). Although minimal response (MR) is not officially a response category in the IMWG criteria, consensus recommendations state that for subjects with relapsed and /or refractory myeloma, MR should be reported separately in clinical trials. Categories of sCR, CR, VGPR, PR, and SD are determined using the IMWG criteria and MR adopted from the EBMT criteria for subjects with relapsed refractory myeloma as outlined below.

Further explanations (noted in superscript) pertaining to particular response criteria are provided in Section 3.2, Clarifications and Modifications. The definition for duration of response is also covered in Section 3.2.18.

3.1.1. Definition of CR

Requires all of the following:

- a. Negative immunofixation of serum and urine (3.24; 3.2.5; 3.2.6; 3.2.19).
- b. Disappearance of any soft tissue plasmacytomas.
- <5% plasma cells in the bone marrow ^(3.2.7).

3.1.2. Definition of sCR

Requires all of the following:

- a. CR as defined above.
- b. Normal FLC ratio (3.2.8).
- c. Absence of clonal bone marrow plasma cell (PCs) by immunohistochemistry, immunofluorescence ^(3,2,9) or 2- to 4-color flow cytometry.

3.1.3. Definition of VGPR

Requires any of the following:

a. Serum and urine M-component detectable by immunofixation but not on electrophoresis (3.2.5; 3.2.11;3.2.12), or

- b. \geq 90% reduction $^{(3.2.10)}_{(3.2.5; 3.2.11)}$ in serum M-protein plus urine M-protein \leq 100 mg/24 hours $^{(3.2.5; 3.2.11)}$
- c. If the serum and urine M-protein are not measurable, a reduction (3.2.10) of >90% in the difference between involved and uninvolved FLC levels (3.2.5; 3.2.13) is required.
- d. In addition to the above criteria, if present at baseline, ≥50% reduction ^(3.2.10) in the size of soft tissue plasmacytomas is also required.

3.1.4. Definition of PR

Requires all of the following:

- a. ≥50% reduction ^(3,2,10) of serum M-protein ^(3,2,5) and reduction ^(3,2,10) in 24-hour urinary M-protein by ≥90% or to <200 mg/24 hours ^(3,2,5).
- b. If the serum and urine M-protein are not measurable, a reduction ^(3,2,10) of ≥50% in the difference between involved and uninvolved FLC levels ^(3,2,5), ^{3,2,13)} is required.
- c. In addition to the above criteria, if present at baseline, ≥50% reduction ^(3.2.10) in the size of soft tissue plasmacytomas is also required.

3.1.5. Definition of SD

Not meeting the criteria for sCR, CR, VGPR, PR, or PD.

3.2. Clarifications and Modifications

As was the case with PD, developing a program to assess response requires adding certain clarifications, minor modifications and additions to the IMWG criteria.

- **3.2.1.** Only subjects with measurable disease at baseline are eligible for assessment of response (i.e., considered in the response-evaluable population). Measurable disease is defined in Section 1.2.1; only legitimated on treatment serum M-protein and urine paraprotein measurements are used for assessment of response. The legitimated on treatment measurements is defined in Section 1.2.6.
- **3.2.2.** CR, sCR, VGPR, PR, MR and SD response categories require no known evidence of progressive or new bone lesions if radiographic studies were performed. Once the program has determined PD for a subject, no subsequent response assessments are performed. For example, a subject who progresses at week 6 cannot have a first response or best response that starts after week 6.

- **3.2.3.** Subjects with measurable disease (defined in Section 1.2.1) in serum (SPEP) and urine (UPEP) need to be followed by both SPEP and UPEP for response assessment and categorization; Except for assessment of CR or better, subjects with measurable disease restricted to the SPEP will need to be followed only by SPEP (i.e., urine M-protein need not show a reduction, but the available urine M-protein values must not meet the criteria for PD); correspondingly, subjects with measureable disease restricted to the UPEP will need to be followed only UPEP (i.e., serum M-protein need not show a reduction, but the available serum M-protein values must not meet the criteria for PD). For example, a subject who has baseline values of 0.1 g/dL of IgG M-protein and 300 mg/24 hrs of urine paraprotein and who subsequently maintains values of 0.1 g/dL and 120 mg/24 hrs will be regarded as achieving a PR; Subjects with measurable disease in either SPEP or UPEP or both will be assessed for response only based on these two tests and not by the FLC assay.
- **3.2.4.** To be considered CR, both serum and urine immunofixation must be carried out and be negative regardless of the size of baseline M-protein in the serum or urine; subjects with negative UPEP values pretreatment still require UPEP testing to confirm CR.
- **3.2.5.** Requires 2 consecutive (i.e., no intermediate values that do not meet the definition of response) assessments made at any time before the institution of any new therapy (i.e., subsequent anti-cancer therapy).
- **3.2.6.** For coding CR in subjects in whom the only measurable disease is by serum FLC levels: it requires a normal FLC ratio (Kappa/Lambda) in addition to CR criteria. However, a normal FLC ratio is not required if the involved FLC level decrease to below detectable level (Kappa<0.5 mg/L or Kappa<0.67 mg/L based on new reagent lot; or lambda<0.6 mg/L). The default reference range of 0.26 to 1.65 will be used to determine normal FLC ratio, if the reference range from central/local laboratory is not available.
- **3.2.7.** If all criteria for confirmed CR were met, except that bone marrow aspirate and biopsy were not performed, and baseline bone marrow evaluation showed <5% plasma cells, then the algorithm accepts this as a CR. If both bone marrow aspirate and bone marrow biopsy were performed at baseline, then both values must have <5% plasma cells for the rule to be applied. For subjects without measurable disease at baseline or subjects whose baseline bone marrow plasma cells percentage is >5%, bone marrow confirmation is required for CR response.

- **3.2.8.** Normal FLC ratio is required for all subjects regardless of whether disease at baseline was measurable on serum, urine, both or neither. However, a normal FLC ratio is not required if the involved FLC level decrease to below detectable level (Kappa<0.5 mg/L or Kappa<0.67 mg/L based on new reagent lot; or lambda<0.6 mg/L). The default reference range of 0.26 to 1.65 will be used to determine normal FLC ratio (Kappa/Lambda), if the reference range from central/local laboratory is not available.
- **3.2.9.** Presence/absence of clonal cells is based upon the kappa/lambda ratio. An abnormal kappa/lambda ratio by immunohistochemistry or immunofluorescence requires a minimum of 100 plasma cells for analysis. An abnormal ratio reflecting presence of an abnormal clone is kappa/lambda of >4:1 or <1:2.
- 3.2.10. Reductions are based on changes from baseline.
- **3.2.11.** VGPR categories require serum and urine studies regardless of whether disease at baseline was measurable on serum, urine, both or neither. For coding VGPR in subjects in whom the only measurable disease is by SPEP, it is not required that UPEP value must meet VGPR criteria, but UPEP test must be performed and not meeting PD criteria whenever SPEP meet VGPR criteria; correspondingly, for coding VGPR in subjects with measureable disease restricted to the UPEP, it is not required that SPEP value must meet VGPR criteria, but SPEP test must be performed and not meeting PD criteria whenever UPEP meet VGPR criteria.
- **3.2.12.** Serum and urine M-protein via SPEP and UPEP must be reported as 0, not detected, or below level of quantification and positive serum or urine immunofixation.
- **3.2.13.** Difference between involved and uninvolved FLC level is defined as absolute value of kappa FLC level minus lambda FLC level in the serum.
- **3.2.14.** Skeletal survey is not required for assessment of response unless clinically indicated. However, if skeletal survey is performed, there should be no indication of disease progression before confirmation of response.
- **3.2.15.** The date of first/best response is the earliest date that all available and required response criteria are met. The date of serum immunofixation response is the initial date of response, not the date of confirmation. The date of urine immunofixation response is the initial date of response, not the date of confirmation. The latest date of response (date at which all criteria were met) among all the relevant response criteria will also be stored in the analysis dataset.

- **3.2.16.** Duration of response (DOR) applies to subjects achieving at least PR by IMWG criteria, and is measured from start of achieving PR (first observation of PR before confirmation) to the time of disease progression, with deaths owing to causes other than progression not counted, but censored. DOR is derived as (date of PD or date of censoring date of first response + 1).
- **3.2.17.** If the first two or more scheduled assessments are missing followed immediately by a confirmed PD (> study day 56), the best response should be SD instead of PD. If best response is assessed as SD, date of best response is not assigned.
- **3.2.18.** Occasionally, the results of the urine immunofixation and UPEP may conflict. If the urine IFE is negative and the UPEP has any value less than 200 mg/24 hrs, the UPEP is disregarded and the urine results are treated as satisfying the requirement for a CR. Similarly, if serum IFE becomes and remains negative, appearance of low level of paraprotein (≤0.5 g/dL or 5 g/L) in SPEP will be disregarded.
- **3.2.19.** A DIRA result of NEGATIVE is treated as equivalent to a negative immunofixation of serum. Since there is no repeat of the DIRA test, we consider a single DIRA test as equivalent of two consecutive immunofixation of serum tests if that indicates a CR.
- **3.2.20.** Subjects with at least one post-baseline disease assessment corresponding to the type of measurable disease at baseline and also not falling into any response category or progressive disease are assigned as response category- stable disease (SD).

4. References

- BGM Durie et al. International uniform response criteria for multiple myeloma. Leukemia 2006
- Rajkumar et al. Consensus recommendations for the uniform reporting of clinical trials: report of the International Myeloma Workshop Consensus Panel 1. Blood 2011

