After EOT, subjects in primary malignancies,	both treatment arms prior to PD will continue to return for and subsequent anti-myeloma therapy. After the primary m OS analysis has occurred and the mPFS for DRd group	disease evaluati clinical cut-off da	ons. After PD is documented, subjects will be follow te (24 September 2018), subject monitoring will be	ved for surviv conducted as	al, PFS2, se per Section	econd
Comuna dia coco	Sample to be sent to central laboratory. IFE and FLC when	X (Repeat on C1D1 if not				
Serum disease evaluations (SPEP)	CR is suspected or maintained. FLC every cycle for subjects with light chain only myeloma.	within 14 days prior to C1D1)	X (for first 2 years and then every 8 wk	s until PD)		
Urine disease evaluations (UPEP)	Sample to be sent to central laboratory. IFE when CR is suspected or maintained.	X (Repeat on C1D1 if not within 14 days prior to C1D1)	X (for first 2 years and then every 8 wk	,		
Calcium, albumin, β ₂ -microglobulin	Sample to be sent to central laboratory. β₂-microglobulin at screening only.	X (Repeat calcium and albumin on	calcium/albumin every cycle for first 2 years and the	•	until PD	

 $CONFIDENTIAL-FOIA\ Exemptions\ Apply\ in\ U.S.$

		Screening						
		Phase	Treatment Phase		Follow-	up Phase		
		11120		EOT	1 0011			
		within 21		within 30		After PD		
		days before		days of	Prior to	(Q16wks)		
	Notes	randomization	Day 1 of each cycle (28-day cycles)	last dose	PD	±2 wks		
		C1D1 if not						
		within 14 days						
		prior to C1D1);						
		don't repeat β2-						
		microglobulin	To confirm CR/sCR, assess MRD, and evaluate PD (if	foscible) Sam	nloc aro			
	For screening (up to 42 days before randomization) fresh		requested at time of suspected CR/sCR and at 12, 18,					
	aspirate or biopsy preferred. If not available, obtain non-		months post C1D1 (+/-1 month). If one of these time p					
	decalcified tissue according to Section 9.2.1.5 Table 9		month of suspected CR, a repeat bone marrow will no					
	and/or FFPE tissue. Fresh biopsy or aspirate (or both)		bone marrow tests will only be required if patient's res	ponse is near (R or better			
Bone marrow	required to confirm CR/sCR. Samples for biomarker		by blood and urine evaluations. See Section 9.2.1.5 for	r additional info	ormation			
aspirate/biopsy	analysis to be sent to central laboratory	X	including timepoints.	1				
Quantitative Ig	See Section 9.2.1.2	X	every 16 weeks	X				

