4.1. Inclusion Criteria

Each potential subject must satisfy all of the following criteria to be enrolled in the study.

- 1. Subject must be at least 18 years of age (or the legal age of consent in the jurisdiction in which the study is taking place).
- 2. Criterion modified as per Amendment INT-2
 - 2.1 Subject must have documented multiple myeloma satisfying the CRAB (calcium elevation, renal insufficiency, anemia and bone abnormalities) criteria (see Attachment 1), monoclonal plasma cells in the bone marrow $\geq 10\%$ or presence of a biopsy proven plasmacytoma, and measurable disease.
 - Measurable disease, as assessed by central laboratory, defined by any of the following:

IgG myeloma: Serum monoclonal paraprotein (M-protein) level ≥1.0 g/dL or urine M-protein level ≥200 mg/24 hours; or

IgA, IgM, IgD, or IgE multiple myeloma: serum M-protein level ≥0.5 g/dL or urine M-protein level ≥200 mg/24 hours; or

Light chain multiple myeloma without measurable disease in serum or urine: Serum immunoglobulin free light chain ≥10 mg/dL and abnormal serum immunoglobulin kappa lambda free light chain ratio.

- 3. Newly diagnosed and not considered candidate for high-dose chemotherapy with SCT due to:
 - Being age ≥65 years, OR
 - In subjects <65 years: presence of important comorbid condition(s) likely to have a negative impact on tolerability of high dose chemotherapy with stem cell transplantation. Sponsor review and approval of subjects under 65 years of age is required before randomization.
- 4. Subject must have an ECOG performance status score of 0, 1, or 2 (refer to Attachment 2).
- 5. Subject must have pretreatment clinical laboratory values meeting the following criteria during the Screening Phase:
 - a) hemoglobin ≥7.5 g/dL (≥5 mM/L; prior red blood cell [RBC] transfusion or recombinant human erythropoietin use is permitted);
 - b) absolute neutrophil count $\geq 1.0 \times 10^9 / L$ (granulocyte colony stimulating factor [GCSF] use is permitted);
 - c) platelet count $\geq 70 \times 10^9 / L$ for subjects in whom < 50% of bone marrow nucleated cells are plasma cells; otherwise platelet count $> 50 \times 10^9 / L$ (transfusions are not permitted to achieve this minimum platelet count);

- d) aspartate aminotransferase (AST) ≤ 2.5 x upper limit of normal (ULN);
- e) alanine aminotransferase (ALT) \leq 2.5 x ULN;
- f) total bilirubin ≤2.0 x ULN, except in subjects with congenital bilirubinemia, such as Gilbert syndrome (direct bilirubin ≤2.0 x ULN);

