9.1.2. Screening Phase

The signed ICF must be obtained before any study-specific procedures are performed. The Screening Phase begins when the first screening assessment is conducted (that was not performed as part of the subject's standard of care). During the Screening Phase, eligibility criteria will be reviewed, and a complete clinical evaluation will be performed as specified in Time and Events Schedule. Screening procedures will be performed within 21 days before randomization; however, results of tests such as skeletal survey, radiologic tests (eg, magnetic resonance imaging [MRI] to document baseline size of known or suspected extramedullary plasmacytomas; ECG; chest x rays [or full chest CT scan]; or bone marrow aspirate or biopsy) performed up to 6 weeks (42 days) before randomization as routine standard of care for the subject's disease can be used. See Attachment 1 for the modified IMWG Diagnostic Criteria.

Subjects <65 years must have known presence of important comorbid condition(s) likely to have a negative effect on the tolerability of high dose chemotherapy with SCT. Documentation of the condition, for example diagnosis of concomitant infectious disease(s), should be provided. Sponsor review and approval of subjects under 65 years of age is required before randomization.

A negative pregnancy test for women of childbearing potential must be documented twice, once within 10-14 days before the first dose and a second time within 24 hours before the first dose of any component of the treatment regimen.

All attempts should be made to determine eligibility of the subject based on the central laboratory results of Screening blood and urine M-protein measurements. In exceptional circumstances, the local laboratory results of blood and urine M-protein measurements may be used to determine eligibility, but only if the results are clearly (eg, 25% or more) above the thresholds for measurability.

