2.9. Analysis Sets

The following analysis sets are defined.

- Intent-to-treat (ITT): defined as subjects who have been randomly assigned to the DRd or Rd group. Analyses of demographics, baseline characteristics and efficacy endpoints will be primarily analyzed based on this population.
- Safety population: defined as subjects who have received at least 1 administration of any study treatment (partial or complete). This population will be used for all safety analyses. The safety analyses grouping will be according to treatment actually received.
- Response-evaluable: defined as subjects who have a confirmed diagnosis of multiple
 myeloma and measurable disease at baseline or screening visit. In addition, subjects must
 have received at least one administration of study treatment and have adequate postbaseline disease assessments. Measurable disease is defined as follows:
 - IgG myeloma: Serum monoclonal paraprotein (M-protein) level ≥1.0 g/dL or urine M-protein level ≥200 mg/24 hours; or
 - IgA, IgD, IgE or IgM multiple myeloma: serum M-protein level ≥0.5 g/dL or urine M-protein level ≥200 mg/24 hours; or
 - Light chain multiple myeloma without measurable disease in serum or urine: Serum immunoglobulin free light chain (FLC) level ≥10 mg/dL and abnormal serum immunoglobulin kappa lambda free light chain ratio.

This population will be used as sensitivity analyses for selective response-related secondary endpoints such as CR or better rate.

- Per-protocol (PP) population: defined as subjects who are randomized and meet all eligibility criteria.
- Pharmacokinetics-evaluable: is defined as subjects assigned to DRd group who received at least 1 administration of daratumumab and have at least 1 pharmacokinetic sample concentration value after the first infusion. All pharmacokinetics analyses are based on the pharmacokinetic evaluable population.
- Immune response-evaluable: is defined as subjects assigned to DRd group who have at least 1 immunogenicity sample obtained after their first daratumumab administration.
- Molecular genetic evaluable: defined as subjects who meet one of the following biomarker criteria for risk assessment based on the next generation sequencing (NGS) data:
 - Standard risk: subjects that are negative (=molecular aberration absent) for all del17p, t(14;16), t(4;14).
 - High risk: subjects that are positive (=molecular aberration present) for any of del17p, t(14;16), t(4;14).

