1.2. Clarifications and Modifications

In order to allow these rules to be applied consistently and to be programmed, the Sponsor has added certain clarifications and modifications for using the IMWG criteria.

- **1.2.1.** Measurable disease is defined in the protocol by at least one of the following measurement: (1) serum M-protein $\geq 1 g/dL$ ($\geq 10 g/L$) or $\geq 0.5 g/dL$ ($\geq 5 g/L$) for subjects with IgA, IgD, IgE or IgM multiple myeloma; (2) urine M-protein ≥ 200 mg/24h; (3) serum FLC assay: involved FLC level ≥ 10 mg/dL (≥ 100 mg/L) provided serum FLC ratio is abnormal.
- **1.2.2.** The reference point for calculating increase and % of increase for M-protein, FLC and bone marrow plasma cells will be the lowest response value and the "lowest response value" does not need to be a confirmed value.
- **1.2.3.** Requires 2 consecutive (i.e., no intermediate values that do not meet the definition of PD) assessments made at any time before the institution of any new therapy (i.e., subsequent anti-cancer therapy). If a subject has an unconfirmed PD

followed by death due to PD within 30 days of unconfirmed PD, or PD (the same parameter as of initial observed PD) observed within 4 weeks after start of subsequent anti-cancer therapy, the unconfirmed PD will be considered as PD.

- **1.2.4.** If nadir serum M-protein is $\geq 50g/L$ ($\geq 5 \text{ g/dL}$), M-protein increases of $\geq 10g/L$ (1g/dL) is sufficient for progressive disease. It does not require meeting "increase of $\geq 25\%$ in the level of serum M-protein".
- **1.2.5.** Any 2 consecutive increase of serum M-protein \geq 5 g/L (\geq 0.5 g/dL) is consistent with progressive disease, assuming that increase of \geq 25% is met or not applicable, even if the serum M-protein level is below measurable disease threshold.
- **1.2.6.** The baseline value for assessing disease progression is the last pretreatment measurement (it applies to SPEP, UPEP, FLC, plasmacytomas and bone lesions except as noticed in Section 1.2.10). For example, if there is a screening value and a Cycle 1 Day 1 value (prior to start of treatment) for M-protein, the program ignores the screening value and uses Cycle 1 Day 1 as the reference point for assessing PD for the first post-treatment results.
- **1.2.7.** The program disregards serum M-protein and urine paraprotein measurements prior to Day 5 after dosing. These tests are considered too soon after dosing to be regarded as legitimate on-treatment values.

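### SAP 2.9 and Attachment 2, 3.2.1 define the response-evaluable population differently; read literally, 3.2.1 scores some eligible subjects as non-responders

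*SAP*

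**What the plan says.** **Entry.** Protocol 4.1, criterion 2.1, requires "Measurable disease, as assessed by central laboratory, defined by any of the following": serum M-protein, urine M-protein or, for light chain disease, free light chain (FLC). Any one is enough. Protocol 9.1.2 asks that eligibility be decided "based on the central laboratory results of Screening blood and urine M-protein measurements".

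**Repeat before dosing.** The Time and Events Schedule marks the screening serum and urine evaluations "X (Repeat on C1D1 if not within 14 days prior to C1D1". A Day 1 value therefore exists for some subjects and not for others.

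**Analysis set.** SAP 2.9 makes a subject response-evaluable if, among other conditions, there is "measurable disease at baseline or screening visit".

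**Algorithm.** Attachment 2, 3.2.1: "Only subjects with measurable disease at baseline are eligible for assessment of response (i.e., considered in the response-evaluable population". For the definition of measurable disease it refers to 1.2.1, which gives thresholds but no time point.

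**Baseline.** SAP 2.5 takes the closest non-missing value on or before first treatment. Attachment 2, 3.2.10, computes reductions from baseline.

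**CR rule.** Attachment 2, 3.2.7: "For subjects without measurable disease at baseline or subjects whose baseline bone marrow plasma cells percentage is >5%, bone marrow confirmation is required for CR".

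**The concern.** The SAP gives two definitions of one population. The word *or* in 2.9 shows that its authors expected screening and baseline to differ for some subjects, so leaving screening out of 3.2.1 changes who is included. Section 3.2.7 adds a second inconsistency, because it sets a marrow requirement for CR in subjects who, under 3.2.1, cannot be assessed for response at all.

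The stricter text is the one that decides who can be scored a responder. CR or better, VGPR or better and ORR come from this algorithm, are analysed in the ITT population, and are steps 1, 2 and 4 of the alpha-controlled sequence in SAP 4.1.1. A subject whom the algorithm declines to assess stays in the ITT denominator and cannot enter the numerator. The size of the response-evaluable sensitivity set also depends on which definition the programmer followed.

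**Working it through.** The plan states no figure on this point, so the check is a reading of the sections together, followed by illustrations on assumed values.

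**1. Can screening and baseline differ?** Yes. Screening runs up to 21 days before randomization and treatment starts within 72 hours after it, so a screening sample can be 21 + 3 = 24 days old at first dose. A repeat is required once the sample is more than 14 days old. Where a repeat exists, it is the closest pre-dose value and becomes the baseline under SAP 2.5. (The exception in 2.5 for SPEP, UPEP and FLC is read here as concerning clock time only; the sentence is not fully clear.)

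**2. One subject under each definition.** Assumed values: IgG myeloma, serum M-protein 1.05 g/dL at screening and 0.95 g/dL on Day 1, urine and FLC below threshold throughout, confirmed on-treatment value 0.40 g/dL. The IgG threshold is 1.0 g/dL.

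- Eligibility: 1.05 ≥ 1.0, met at screening.
- SAP 2.9: measurable at screening, so response-evaluable.
- Attachment 2, 3.2.1, with baseline as in SAP 2.5: 0.95 < 1.0, so not assessed for response.
- Fall from screening: (1.05 − 0.40)/1.05 = 61.9%.
- Fall from Day 1: (0.95 − 0.40)/0.95 = 57.9%.

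Both falls pass the 50% serum criterion for PR. The choice of reference value does not matter here; only the entry condition in 3.2.1 turns a response into a non-response.

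**3. Size.** Let x be the share of subjects who drop below every threshold between screening and Day 1. If x and the true response rate in these subjects are the same as elsewhere and equal in both arms, each ITT rate is multiplied by (1 − x), and so is the difference between arms. The documents do not give x; the 90% rate and 20-point difference below are assumptions too.

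| x | subjects of 730 | loss on a 90% rate | 20-point difference becomes |
|---|---|---|---|
| 0.5% | 3.7 | 0.45 points | 19.9 |
| 1% | 7.3 | 0.9 points | 19.8 |
| 3% | 21.9 | 2.7 points | 19.4 |
| 5% | 36.5 | 4.5 points | 19.0 |

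**4. Does simply adding screening to 3.2.1 cause a new problem?** It can. Take assumed urine M-protein of 210 mg/24 h at screening and 190 on Day 1, with serum not measurable. Under 3.2.3 only urine is followed. PR in 3.1.4 accepts either a 90% urinary reduction or a value under 200 mg/24 h. Two consecutive values of 185 would then qualify, although the fall from baseline is (190 − 185)/190 = 2.6%. Confirmation on two assessments does not prevent this.

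**The case against.** Three stronger readings are tempting, and the documents do not support them.

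*That the algorithm requires measurable disease on Cycle 1 Day 1.* A reader might take this from Attachment 2, 1.2.6, where "the program ignores the screening value and uses Cycle 1 Day 1 as the reference point". That sentence goes on to limit itself to assessing progression, and the section opens by defining baseline for that purpose. No section says measurability for response is judged on Day 1. The link to baseline comes from SAP 2.5, and a repeat is required only when the screening sample is too old.

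*That such a subject can never be a responder.* The parenthesis in 3.2.1 can be read as pointing to the set defined in 2.9, which would admit the subject. Its reference to 1.2.1 leads to the protocol criterion, which is judged at screening. Section 3.2.7 provides for CR without measurable disease at baseline. Sections 3.2.8 and 3.2.11 also mention disease measurable in neither serum nor urine, although that may mean FLC-only subjects.

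*That many properly enrolled subjects are affected.* One qualifying marker is enough, so the subject must fall below all of them. Protocol 4.2 also says a subject who loses eligibility before first dose should be excluded. That applies only if the Day 1 result is known before dosing; the sample goes to the central laboratory, and turnaround is not stated.

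It is also fair to say that no directional bias or type I error inflation is shown, and that SAP 4.3.1.2 already plans an investigator-assessed response analysis. What remains is that the two definitions differ in words, 3.2.7 does not fit 3.2.1, and a programmer could follow either.

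**Conclusion.** The inconsistency is real and the consequence is conditional. Under the literal reading of 3.2.1 with SAP 2.5, an eligible subject who was measurable at screening but below every threshold on a Day 1 repeat is scored a non-responder; under 2.9 the same subject is assessed. The number is unknown from the documents, probably small, and probably similar in the two arms, in which case rates and their difference shrink by the same small factor.

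The 3.2.1 condition governs response only and does not enter the determination of PFS. The protocol reports superiority on PFS and OS as already established. What is at stake is the accuracy of the reported response rates and the composition of the sensitivity population, including in the final CSR update.

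**What to change.** In SAP Attachment 2:

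- In 1.2.1 and 3.2.1, state that measurability for response is met at screening or baseline, as in SAP 2.9. Limit the wording to response, because measurability also decides whether FLC can define progression (1.1.1 c) and that rule should not shift by accident.
- Keep the last pretreatment value as the reference for reductions.
- Reword 3.2.7 to match.
- State that when the last pretreatment urine M-protein is already below 200 mg/24 h, being under that level does not by itself establish PR.
- Correct the cross-reference in 3.2.1 for legitimate on-treatment measurements: the rule is in 1.2.7, not 1.2.6.

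The cost is a few lines of text, one flag for measurability and one condition for the urine guard. The remaining drawback is that reductions for these few subjects are computed from a slightly sub-threshold baseline. If the program already follows 2.9, aligning the definitions is documentation only, and the urine guard still has to be checked in the code. If it was run on the stricter rule, list the affected subjects by arm and report CR or better, VGPR or better and ORR both ways.
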